### 13.4 Version 6.1

- Section 6.1.3 (Open-label Period): Day 792 corrected to Day 729.
- Section 6.2.5.2 (Collection of electronic Patient-reported Outcomes Assessments): Reference to paper collection was removed.
- Table 5 (Open-label Period Procedures for AChR-Ab+ and MuSK-Ab+ Populations): Day 730 corrected to Day 729.
- Table 5: Addition of OLP Day 15 C-SSRS at Day 15 (as this was erroneously removed from Protocol V6.0).
- Table 5: Removal of IP Administration at Day 1093 ( $\pm 20d$ ) or EDV to provide consistency with verbiage in Section 6.1.3 and 6.1.4, respectively.
- Table 5, footnote "h" text separated into text for footnotes "h" and "i" as this was erroneously captured as 1 footnote instead of 2 in the previous version. Due to this update, previous footnotes "i" and "j" have been appropriately updated to "j" and "k", respectively.
- Table 5, Column "OLP Week 156, Day 1093 ( $\pm 20d$ ) or EDV", superscript letter "j" updated to "k" to corresponded to applicable footnote text.

- Section 13 (Protocol Changes): Changes under Version 6.0 updated to remove inaccurate changes: 1) deletion of change related to Section 6.3.2 title (as no change occurred); 2) deletion of change related to removal of [REDACTED] (as this remains included in the study).

### 13.5 Version 6.0

- Global change: The word “participant(s)” is changed to “subject(s)” for consistency.
- Global change: All brand names of the medications throughout the protocol have been removed for consistency.
- Title page: National Clinical Trial (NCT) number is added. Sponsor information and Responsible Medical Officer have been updated to reflect staff change.
- Sponsor Signature page: A new Sponsor page was included with Medical and Biostatistics Representative information.
- List of Appendices and Appendices: Updated to include listing of Opportunistic infections.
- List of Abbreviations page, Section 5.2 (Exclusion Criteria), and Section 7.5.2 (Prohibited Medications and Treatments): Updates are made to include neonatal fragment crystallizable (Fc) receptor blockers since it is a new stable IST treatment option for chronic therapy and rescue.

- Section 1 (Synopsis): Protocol number added as an independent row for consistency.
- Section 1 (Synopsis), Section 3.2.2 (Secondary Endpoints), Section 4.4 (Rationale for Endpoint Selection), and Section 9.4.2 (Analysis of Key Secondary Efficacy Endpoints): Key Secondary Endpoint number 2 has been updated to be maintain consistency with the primary analysis and to utilize more observed data.
- Section 1 (Synopsis), Figures 1, 2, and 3, Section 4.1 (Study Design), Section 6.1.3 (Open-label Period), Table 5 (Open-label Period Procedures for AChR-Ab+ and MuSK-Ab+ Populations [columns and footnote]), Section 6.3.1 (Discontinuation of Treatment), Section 6.3.2 (Withdrawal from Study), Section 6.5 (End of Study), and Table 6 (Description of Investigational Products and Dosing Regimens): Updated information on blinding and extension of OLP to allow long-term safety and efficacy data collection.

- Section 2.1.3 (Supportive Clinical Data for Inebilizumab) and 2.2 (Study Rationale): Updated information about inebilizumab to inform that it has been approved in other countries.
- Sections 3.2.2 (Secondary Endpoints), Section 4.4 (Rationale for Endpoint Selection), and Section 9.4 (Methods for Statistical Analyses): Key secondary endpoint updated to clarify timeline of rescue therapy use for AChR-Ab+ and MuSK-Ab+ subjects.
- Section 4.2 (Dose and Treatment Regimen Rationale): Updated to clarify there is no expected difference in inebilizumab PK between subjects with NMOSD and MG, the proposed dose regimen is expected to be well-tolerated and achieve similar PD effect in subjects with MG.
- Section 4.3 (Rationale for Study Population); Tables 3, 4 and 5 (Schedules of Study Assessment for AChR-Ab+ population, MuSK-Ab+ population and Open-label period and footnotes); Section 6.2.5.2 (Timing of Efficacy Assessments); and Section 9.4 (Methods for Statistical Analyses): The time was changed from 12 hours to 6 hours to allow for shorter time for subjects to hold acetylcholinesterase inhibitors while continuing to safeguard the collection of MG-ADL. Expanded Pyridostigmine to Acetylcholinesterase inhibitors. Clarified corticosteroid dose to include prednisone or its derivatives.
- Section 5.1 (Inclusion Criteria), Section 6.2.4 (Verification of Eligibility): Updated the MG-ADL scoring criteria to ensure adequate non-ocular scoring across a broad range of MG-ADL.
- Section 5.2 (Exclusion Criteria): Instruction to refer reader to Inclusion Criterion #7 in Exclusion Criterion #13 “b.” New drug class added under bullet point 11 and 12 to broaden the range of medications in these categories. Exclusion criterion was further clarified. 2 new exclusion criteria have been added to ensure that subjects entering the study are clinically and IST stable to ensure accurate baseline assessments. Hepatitis C exclusion criterion (Section 5.2, criterion #24) has been expanded to exclude subjects with a history of untreated hepatitis C infection or who have tested positive for HCV, unless the subject is considered to be cured following antiviral therapy.
- Section 6.1.1 (Screening Period), and footnote “c” of Table 2 (Screening Procedures [Visit 1]): Language updated to allow for the use of reference ranges provided by both labs used in the study. Clarified that re-screened subjects are not required to repeat serostatus testing as long as positive serostatus screening result within prior 6 months was done using cut-off points associated with the validated tests.
- Section 6.1.4 (Safety Follow-up Period): New section added to describe follow-up of subjects who do not enter OLP or discontinue IP during OLP. New Table 6: Safety Follow-up Period, was added to this section. This information is updated in Section 1 (Synopsis), Section 4.1 (Study Design), and Figure 2.
- Section 6.1.5.1 (Remote Visits and/or Procedures), Section 6.1.5.2 (Clinical Deterioration Visits), Section 6.1.5.3 (Unscheduled Visit), and Tables 3, 4, and 5 (Schedules of Study Assessment for AChR-Ab+ population, MuSK-Ab+ population and Open-label period

columns and footnotes): Have been added to clarify the difference between the Remote Visits and/or Procedures, Unscheduled Visit and the Clinical Deterioration visit.

[figure not shown]
- Section 6.1.5.3 (Unscheduled Visit): Updated to differentiate between Clinical Deterioration Visit and Unscheduled Visit.
- Section 6.1.5 (Special Visit Types) added to describe remote/home visits, clinical deterioration visits, and unscheduled visits. New table (Table 7: Procedures for Special Visit Types) was added to Section 6.1.5.
- Section 6.2.1 (Informed Consent): The section is updated to clarify that 2 separate ICFs need to be obtained, one each for the RCP and the OLP.
- Footnote I for Tables 3, 4, and 5 (Schedules of Study Assessment for aChR-Ab+ population, MuSk-Ab+ population and Open-label period): Updated to allow for flexibility of site dispensation of corticosteroids.
- Section 6.2.5.1 (Role of the Independent Rater): Split into 2 additional Sections 6.2.5.2 (Collection of Electronic Patient-reported Outcomes [ePRO] Assessments) and Section 6.2.5.3 (Timing of Efficacy Assessments), for clarity of the information presented. This addition of subsections caused re-organization of level 4 headers under the 6.2.5 level 3 header.

- Section 6.2.6.1 (Electrocardiogram): Added RR to include another interval for clarity of ECG information.
- Section 6.2.7 (Clinical Laboratory Assessments): Added Hepatitis C antibody under Viral Serology for consistency within the document.
- Section 6.3.1 (Discontinuation of Treatment): Updated to accommodate current study design.
- Section 6.3.2 (Withdrawal from Study): Updated information for clarity.
- Tables 3 (Randomized Controlled Period Schedule of Study Assessments for the AChR-Ab+ Population), 4 (Randomized Controlled Period Schedule of Study Assessments for the MuSK-Ab+ Population), and 5 (Open-label Period Procedures for aChR-Ab+ and MuSK-Ab+ Populations): Re-organized information regarding procedures and blood sampling into a new footnote h.
- Table 8 (Description of Investigational Products and Dosing Regimens): Updated manufacturer information.
- Section 7.1.1.1 (Investigational Product Inspection) and Section 7.1.3 (Reporting Product Complaints): Updated contact information of the Sponsor's Quality Assurance.
- Table 10 (Randomized Controlled Period Prednisone Tapering Schedule): Study Day information updated for clarity.

[figure not shown]

- Section 7.2.1 (Oral Prednisone Taper) and Section 7.2.2 (Rescue Medication): Verbiage changed from study drug to IP for clarity.
- Section 7.3.2 (Randomization Strategy and Procedures): Language updated to clarify that stratification should be based on Day 1 QMG.
- Section 7.5.2 (Prohibited Medications and Treatments): B-Cell Depleting Therapies and Other immunosuppressive medications and monoclonal antibody medications were updated to clarify list of medications prohibited during the study.
- Section 8.3 (Reporting Adverse Events), Section 8.4.1 (Pregnancy), and Section 8.4.2 (Overdose or Misuse): Updated Sponsor's contact information for SAE form and safety reporting procedures.
- Section 8.5 (Adverse Events of Special Interest): Reference was added for Appendix 4. removed table to make easy reference by calling out Section 8.3 with contact information. Added IRR to the list of considered AESIs.
- Section 9.3 (Analysis Sets): Updated information in Per-protocol Analysis Set to better evaluate treatment effect in efficacy and safety data.
- Section 9.4 (Methods for Statistical Analyses): Updated to clarify the definition of primary estimand and supplemental estimands for the primary and key secondary endpoints.
- Section 10.1 (Regulatory and Ethical Considerations): Prior subtitle for this section was Good Clinical Practice. Added more details for more clarification.
- Section 11.3 (Audits): Language was updated for clarification.
- Section 14 (References): Updated per literature search.

### 13.6 Version 5.0

- Cover page – Responsible Medical Officer have been updated to reflect staff change.
- Section 1 (Synopsis), 4.1 (Study Design) and Figure 1 (Study Flow Diagram and Footnote): Approximate number of subjects in the study has been updated (up to additional 16 AChR-Ab+ subjects and 2 additional MuSK-Ab+ were added), in order to account for potential increased heterogeneity in baseline therapy in Japan. The total number represent upper estimated limit and may be reduced based on number of subjects enrolled in Japan.
- Section 1 (Synopsis), 3.3.2 (Exploratory Endpoints) and 6.2.8 (Pharmacokinetics, Pharmacodynamic, Immunogenicity, and Biomarker Evaluations):   

- Section 1 (Synopsis) and 4.1 (Study Design): Approximate number of sites have been updated.

- Section 2.1.5 (Anticipated Study Benefits and Risks), 4.1 (Study Design), 4.3 (Rationale for Study Population), 6.1.3 (Open-label Period), 7.5.1 (Immunosuppressive Medications During the Screening Period): Updated to include the allowance and guidelines for use of tacrolimus in Japan.

- Sections 4.1 (Study Design) and 7.3.2 (Randomization Strategy and Procedures): Stratification criteria for Japan were changed to align with the allowance of tacrolimus in Japan to maintain balanced randomization of Japanese subjects.
- Figures 2 and 3 (Randomization Schemes for AChR-Ab+ population and MuSK-Ab+ population): header of figures have been updated from “Randomization Scheme” to “Design Scheme” for a more accurate representation of what these figures depict.
- Section 5.1 (Inclusion Criteria 1): Guidance on consent in Japan where legal adult age is >18 have been rewarded to include general guidance for all countries where legal adult age is > 18. Additionally, this was moved from under Inclusion Criterion #1 to under Inclusion Criterion #2 where the informed consent is discussed.
- Section 5.1 (Inclusion Criteria 7c), 5.2 (Exclusion Criteria 12b), 7.5.1 (Immunosuppressive Medication During the Screening Period) and 7.5.2 (Prohibited Medications and Treatments): Updated to allow the use of tacrolimus in Japan only since tacrolimus in Japan is part of the standard of care for MG.
- Section 6.1.1 (Screening Period): Updated to allow screening extension to accommodate delays in study supplies (eg, lab kits supply delay from central lab).
- Section 6.1.1 (Screening Period) and Table 2 (Screening Procedures, footnote c): Guidelines were added for re-screened subjects regarding repeat serostatus testing.
- Section 6.1.2.1 (Remote Visits or Procedures): Section was added to accommodate exceptional circumstances under which particular study visits or procedures may be performed remotely (eg, due to COVID-19 restrictions) and with agreement of the medical monitor.
- Section 6.1.3 (Open-label Period): Updated to include guidance for subjects on tacrolimus in Japan.

- Section 6.2.1 (Informed Consent): Guidance for countries where legal adult age is > 18 years has been added. Additionally, Clarification was added that participation and informed consent forms for [REDACTED] and use of leftover blood samples for future research are only done if applicable in that country as not all countries will be participating in these optional substudies.
- Section 6.2.5.3 (Myasthenia Gravis Quality of Life-15, revised): Total score for MGQOL-15r was corrected from 45 to 30 and name of assessment was corrected from MG-QOL15r to MGQOL-15r throughout for consistency.
- Section 6.2.7 (Clinical Laboratory Assessments): Revised to state that in some cases, safety labs can be done locally if preapproved by the Sponsor Medical Monitor.
- Table 6 (Description of Investigational Products and Dosing Regimens): Legal name of DP manufacturer had changed and was therefore updated in the table.
- Section 7.1.1.3 (Dose Preparation): Clarification was added regarding total time allowed for room temperature storage.
- Section 7.1.1.4 (Dosing and Administration): Reference to new Table 7 was added and “approximately” was added to the duration under IP infusion instructions.
- Section 7.1.3 (Reporting Product complaints): Phone numbers have been removed since these may be subject to change.
- Table 7 (Predose IV Corticosteroid Dose Conversion): was added to the protocol to provide guidance on alternatives to IV methylprednisolone and the equivalent doses. Table numbers of previous tables 7, 8 and 9 have been updated accordingly.
- Table 9 (Corticosteroid Dose Conversion): Updated to include the equivalent dose of hydrocortisone. Table number was updated from 8 to 9.
- Section 7.2.2 (Rescue Medication): Updated to clarify that rescue therapies should be recorded on study’s rescue therapy dedicated eCRF pages.
- Section 8 (Safety Assessment): Clarification was added to Adverse Event section that MG exacerbation are an endpoint in the study and therefore will not be recorded as AEs or SAEs (with the exception of exacerbations that involve myasthenic crisis or death).
- Section 8 (Safety Assessment): Serious adverse event definition for hospitalization was updated to remove the requirement for > 1 day or overnight length of hospital stay, based on request received from the Denmark regulatory authority.
- Section 8.4.2 (Overdose or Misuse): Language has been shortened and updated to include only IP and remove steroids and infusion premedication from overdose definition.
- Section 8.5 (Adverse Event of Special Interest): Updated to include reporting procedure for AESI.
- Section 9 (Statistical Considerations): Number of subjects have been updated to allow additional 16 AChR-Ab+ subjects and 2 additional MuSK-Ab+; additional subgroup analyses information was provided.

- Section 9.4.4 (Analysis of Exploratory Efficacy Endpoints): [REDACTED].
- Section 9.4.6 (Subgroup Analyses): Updated to clarify the detailed subgroups in the analyses; added a subgroup analysis of Racial/ethnic subgroups as needed for national/regional regulatory filings.
- Section 10.1 (Good Clinical Practice): Reference to the Declaration of Helsinki was removed as the current version of Declaration of Helsinki was not adopted by the FDA.
- Section 10.5 (Biological Specimens and Data): Updated to clarify that the mentioning of future use of leftover samples is only in applicable countries.
- Section 11.3 (Audits): Language was updated to include inspectors/inspections (in addition to auditors/audits).
- Section 11.4.3 (Record Retention): Revised to accurately capture ICH E6 wording.

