### 3.3 Exploratory Objectives and Endpoints

#### 3.3.1 Exploratory Objectives

#### 3.3.2 Exploratory Endpoints

## 4 STUDY PLAN

### 4.1 Study Design

This study is a Phase 3, randomized, double-blind, multicenter, placebo-controlled study to be conducted at approximately 120 study sites. Approximately 230 subjects (188 subjects with AChR-Ab+ MG and 42 subjects with MuSK-Ab+ MG) are planned to be enrolled. To account for the allowance of tacrolimus in Japan and potential introduction of heterogeneity in baseline therapy, the total number of subjects represents an upper estimated limit for recruitment and may be reduced, depending on the total number of Japanese subjects enrolled.

Subjects with MG who are positive for anti-AChR or anti-MuSK antibodies will be enrolled. Subjects with MGFA classification II, III, or IV disease at the time of screening and randomization; MG-ADL score at screening and randomization between 6 and 10 with > 50% of this score attributed to non-ocular items, or an MG-ADL score  $\geq 11$ ; QMG score  $\geq 11$  at the time of screening and randomization; and use of a corticosteroid and/or non-steroidal immunosuppressant will be included in the study. These criteria define a population of subjects with generalized MG and inadequate symptom control.

Within each population, subjects will be stratified by region first (non-Japan vs Japan). In the non-Japan population, subjects will be further stratified according to baseline disease severity (“Day 1 QMG score = 11-15” vs “Day 1 QMG score  $\geq 16$ ”) and baseline corticosteroid use (“prednisone > 5 mg/day” vs “prednisone  $\leq 5$  mg/day”), and randomized 1:1 to receive either IV inebilizumab or placebo within each stratum (Figure 1). To quantify disease severity for stratification purposes, the QMG was chosen over the MG-ADL because the results are more likely to be consistent between individuals since the QMG is based on objective examination and the MG-ADL is based on subjective reporting.

In the Japan population, no further stratification will be applied due to the small sample size, and subjects will be randomized 1:1 to receive either IV inebilizumab or placebo. Subjects will be allowed to enter the study on a standard of care regimen, including acetylcholinesterase inhibitors, corticosteroids, and/or azathioprine, mycophenolate mofetil, and mycophenolic acid. In Japan, subjects will also be allowed to enter the study on tacrolimus.

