### 9.2 Determination of Sample Size

The primary endpoint is the change from baseline in MG-ADL score at Week 26 in the overall study population (ie, the AChR-Ab+ and MuSK-Ab+ populations). Sample sizes were estimated using a 2-sided t-test. Approximately 230 subjects (188 subjects with AChR-Ab+ MG and 42 subjects with MuSK-Ab+ MG) will be randomized in a 1:1 ratio to either inebilizumab or placebo. This sample size will provide more than 95% power to detect a true mean (population) treatment difference of 2 in the overall study population with a 2-sided 0.05 alpha level, assuming a common standard deviation of 4 using a 2-sided t-test.

The sample size of AChR-Ab+ subjects was also estimated using a 2-sided t-test, which will provide at least 90% power to detect a true mean (population) treatment difference of 2 in change from baseline of MG-ADL with a 2-sided 0.05 alpha level. The sample size of MuSK-Ab+ subjects was estimated based on the feasibility of the enrollment. Assuming a common standard deviation of 4 and a 2-sided 0.05 alpha level, the minimum detectable difference in the MuSK-Ab+ population is 2.5.

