The primary endpoint will be analyzed using a mixed-effects model for repeated measures (MMRM) analysis with covariates of treatment group, baseline antibody status (AChR-Ab+ or MuSK-Ab+), visit, the interaction of visit and treatment group, baseline steroid use, baseline QMG score, and baseline MG-ADL score. The estimate of the treatment effect estimator will be based on a contrast from this MMRM model. The variance-covariance matrix will be assumed to be unstructured. If the procedure doesn't converge, then a compound symmetric variance-covariance matrix will be applied.

To assess the robustness of the treatment effect, for each estimand, additional sensitivity analyses utilizing multiple imputation (MI) approaches will also be conducted with the missing data imputed for the subjects who discontinue the study early based on the different missing data mechanism assumptions, including those expected to be more conservative such as missing not at random. For example, the missing data would be imputed

[REDACTED]

[REDACTED]. Full details of the analyses will be prespecified in the SAP.

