#### 9.4.6 Subgroup Analyses

To explore the consistency of treatment effect, subgroup analyses will be performed for the primary and the key secondary endpoints in the following subgroups:

- Baseline antibody type (AChR-Ab+ vs MuSK-Ab+).
- Gender (Male vs Female).
- Age ( $\geq 18 < 65$  years vs  $\geq 65$  years).
- Baseline MG disease duration ( $< 5$  years vs  $\geq 5$  years).
- Baseline steroid use (prednisone  $\leq 20$  mg/day vs prednisone  $> 20$  mg/day).
- Baseline IST use (steroid only vs steroid plus 1 other IST).
- Baseline QMG score ( $\leq 15$  vs  $\geq 16$ ).
- Baseline MGFA class (Class II vs III vs IV).
- Region (US vs non-US; Japan vs non-Japan; China vs non-China; Asia vs non-Asia; EU vs non-EU).
- Racial/ethnic subgroups as needed for national/regional regulatory filings.

All the analyses will be performed on the FAS. Additional subgroup analyses by the length of inebilizumab exposure may be performed on the Any Inebilizumab Analysis Set. Details would be included in the SAP.

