3.3.2 Demographics, Baseline Characteristics, and Medical History

Demographic data and key baseline characteristics will be summarized using descriptive statistics on FAS. The demographic data and key baseline characteristics will include but are not limited to the following variables.

- Demographic: age, gender, race, ethnicity, height, weight, and body mass index.
- Baseline Characteristics: baseline antibody status, MG-ADL score, QMG score, MGFA class, MGC Score, PGIC, MGQOL-15r score, Steroid use, non-steroid IST use and CD20+ B-cell count etc.

Significant medical history findings will be summarized by MedDRA system organ class (SOC) and preferred term (PT).

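### The protocol's primary and key secondary MMRMs adjust for baseline steroid use but list no term for baseline non-steroidal immunosuppressant use, a small, cheaply avoided possible loss of precision

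*Protocol*

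**What the plan says.** Protocol 4.1 explains the total of about 230 (188 AChR-Ab+, 42 MuSK-Ab+) with the words "To account for the allowance of tacrolimus in Japan and potential introduction of heterogeneity in baseline therapy", and says the number may be reduced depending on Japanese enrolment. The change history (13.6, version 5.0) gives the same reason, "in order to account for potential increased heterogeneity in baseline therapy in Japan", for a planned increase of up to 16 AChR-Ab+ and 2 MuSK-Ab+ subjects. Version 7.0 (13.3) later set the numbers at 188 and 42.

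Inclusion criterion 7 allows steroids only, one non-steroidal IST only, or both. Protocol 4.5 makes the steroid taper independent of clinical status, and Table 12 brings every tapered subject to 5 mg/day by Week 24 at the latest. Sections 4.3 and 7.5.2 keep the IST dose unchanged through the randomized period, apart from reductions for safety.

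The primary MMRM (9.4.1) has treatment, antibody status, visit, visit-by-treatment, and "baseline steroid use, baseline QMG score, and baseline MG-ADL score". The key secondary models (9.4.2) use the same list, without antibody status in the single-antibody populations, and 9.4.3.2 builds on it. None names IST use. Randomization (7.3.2) is stratified by Japan vs non-Japan and, outside Japan, by QMG and steroid dose.

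IST use is nevertheless recorded. SAP 3.3.2 lists "Steroid use, non-steroid IST use and CD20+ B-cell count" among the baseline characteristics, and protocol 9.4.6 plans a subgroup analysis by "Baseline IST use (steroid only vs steroid plus 1 other IST".

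**The concern.** The plan recognises that background therapy varies and lets this influence the number of subjects. By Week 26 a steroid-only subject who was tapered has 5 mg/day of prednisone left, while a subject on a combination has that plus an IST at its entry dose. If IST use predicts MG-ADL or QMG change, that variance stays in the residual of the listed models and widens the interval for the treatment contrast.

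The steroid covariate covers part of this, because anyone who enters without a steroid must be on an IST. It cannot separate steroid-only from combination subjects who enter on the same steroid dose. The planned subgroup analysis does not improve the precision of the main contrast, and it has no category for subjects on an IST alone.

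At stake is a modest efficiency gain from a variable already in the database.

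**Working it through.** **Inputs from the documents.** Protocol 9.2 sizes the trial "with a 2-sided 0.05 alpha level, assuming a common standard deviation of 4 using a 2-sided t-test", with a 2-point difference and 115, 94 and 21 subjects per arm (overall, AChR-Ab+, MuSK-Ab+).

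**Inputs assumed.** The documents give neither the prevalence p of IST use nor its shift d in mean Week 26 change. I take p from 5% to 50% and d of 1 or 2 points, with no overlap between IST and the existing covariates.

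**Step 1: the plan's own figures.** SE = 4 × √(2/n), with power from the noncentral t.
- Overall: SE = 4 × √(2/115) = 0.527, 2/SE = 3.79, power 96.5%. The plan says "This sample size will provide more than 95% power to detect a true mean (population) treatment difference of 2 in the overall study population". Reproduced.
- AChR-Ab+: SE = 4 × √(2/94) = 0.583, 2/SE = 3.43, power 92.65%. The plan says "at least 90% power to detect a true mean (population) treatment difference of 2 in change from baseline of MG-ADL". Reproduced.
- MuSK-Ab+: SE = 4 × √(2/21) = 1.234. The smallest observed difference reaching p < 0.05 is 2.02 × 1.234 = 2.49, matching the stated 2.5.

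**Step 2: what an IST term could explain.** R² = p(1−p)d²/16. Equivalent subjects = 230/(1−R²) − 230. Power uses residual SD = 4√(1−R²), before the cost in Step 3.

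| p | d | R² | Subjects of 230 | Power overall | Power AChR-Ab+ |
|---|---|---|---|---|---|
| 5% | 1 | 0.3% | 0.7 | 96.57% | 92.72% |
| 5% | 2 | 1.2% | 2.8 | 96.70% | 92.93% |
| 25% | 1 | 1.2% | 2.7 | 96.70% | 92.93% |
| 25% | 2 | 4.7% | 11.3 | 97.18% | 93.74% |
| 50% | 1 | 1.6% | 3.7 | 96.75% | 93.02% |
| 50% | 2 | 6.3% | 15.3 | 97.38% | 94.08% |

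If the IST variance instead came on top of SD 4, the worst case in the table (p = 50%, d = 2) gives SD = √(16 + 1) = 4.12. Power is then 95.6% overall and 91.1% in AChR-Ab+. Both stated bounds still hold.

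**Step 3: what the term costs.** As a single-visit approximation, one more parameter inflates variance by about 1/(N − 4). It pays off when R² exceeds that cost, which at p = 50% means d > 8 × √cost.
- Overall: 1/226 = 0.44%, break-even d = 0.53.
- AChR-Ab+: 1/184 = 0.54%, break-even d = 0.59.
- MuSK-Ab+: 1/38 = 2.6%, break-even d = 1.30.

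**The case against.** The case against has real force, and most of it stands.

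- **The sponsor's reason is narrower than ISTs in general.** Sections 4.1 and 13.6 speak of tacrolimus in Japan. Extending the argument to azathioprine and mycophenolate is my inference from criterion 7 and the taper.
- **More subjects were not the only answer.** A reader might infer so, but Japan vs non-Japan is the first stratification factor, and 13.6 ties the change in Japan stratification to tacrolimus. Dose stability rules and subgroup analyses by IST and region are also planned.
- **The figure of 18 should not carry the argument.** It is a planning increment (16 + 2) in the log of a superseded version, not a count of subjects enrolled. A covariate would match it only with R² = 18/230 = 7.8%, a shift of 8 × √0.078 = 2.2 points at p = 50%, larger than the treatment effect the trial is powered for. More subjects and a covariate are alternative remedies, so choosing one does not contradict the other.
- **Chance imbalance in IST use is not a second harm.** At p = 50% its SD is √(0.5/94) = 0.073 in AChR-Ab+ and √(0.5/21) = 0.154 in MuSK-Ab+. With d = 2 it moves the estimate by 0.146 and 0.309 points (1 SD). Divided by the SEs of 0.583 and 1.234, both equal 0.25, and 0.25² is the same 6.3%. The SE already includes it, and randomization removes bias.
- **The R² values are probably too high.** They ignore the steroid, QMG and MG-ADL terms, and criterion 7 links steroid and IST use by construction.

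What remains is that the listed models omit a recorded baseline variable whose effect is plausible by Week 26, and that in the two larger analyses including it costs almost nothing.

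**Conclusion.** The point holds as an inexpensive improvement in precision. The protocol's listed MMRM covariates omit baseline non-steroidal IST use. Whether the SAP's models do so cannot be seen, because that text is redacted.

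No stated figure, error rate or estimand is wrong, and the treatment contrast is not biased. Over the assumed range, adjustment raises power from 96.5% to at most about 97.4% overall, and from 92.65% to at most about 94.1% in AChR-Ab+. At 50% prevalence this is worth about 4 subjects for a 1-point shift and 15 for a 2-point shift. These figures rest on assumed prevalence and shift, SD 4, and no overlap with existing covariates. Overlap would shrink them.

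A reader might expect the small MuSK-Ab+ analyses, tested last, to gain most. The arithmetic does not support that: the term helps there only if the shift exceeds about 1.3 points.

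**What to change.** First confirm what the unredacted SAP models contain. If IST use is absent:

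- Pre-specify baseline non-steroidal IST use (none vs any of azathioprine, mycophenolate mofetil, mycophenolic acid or tacrolimus) as a fixed effect in the overall and AChR-Ab+ MMRMs of protocol 9.4.1 and 9.4.2, and in SAP 3.4.2.2 and 3.4.3.2. Carry it into the matching models of protocol 9.4.3.2, which reuse the list.
- In the MuSK-Ab+ MMRMs (42 subjects), keep the listed covariates for the main analysis and add IST use only as a sensitivity analysis.

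The cost is one parameter, about 0.5% of variance in the two larger analyses, with little or no gain if IST use is not prognostic beyond the existing terms. No new data, visits or subjects are needed. Protocol 9.1 allows final SAP amendments before database lock; the change must be fixed before unblinding.
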